6. STUDY PROCEDURES

6.1 Schedule of Evaluations

Assessment	Screening Visit-1 (Day-14 to Day-1)	Baseline Visit 1 (Day 0)	Tx Visit 2 (W1)	Tx Visit 3 (W2)	Tx Visit 4 (W3)	Tx Visit 5 (W4)	Tx Visit 6 (W5)	Tx Visit 7 (W6)	Tx Visit 8 (W7)	Tx Visit 9 (W8)	Tx Visit 10 (W9)	Follow-up Final Visit (W16)
Verbal consent	X											
Informed Consent Form		X										
Demographics	X											X
Medical Chart Review	X											
Current Medications	X	X										
Inclusion/Exclusion Criteria	X											
Enrollment/ Randomization		X										
Adverse Events		X	X	X	X	X	X	X	X	X	X	
Questionnaires		X								X	X	
Heart measurement rate		X								X	X	
Blood draw		X								X		

6.2 Description of Evaluations

6.2.1 Screening Evaluation

During clinic hours, research staff at the oncology practices will introduce potentially eligible patients to the study using a verbal script. Interested patients (having received a letter, flyer or referral) will call our office and receive an initial phone screening to assess age, stage, and Hebrew or Arabic language use. If initial criteria are met, an in-person visit will be scheduled either in our University office or at one of the 3 hospital recruitment sites where private rooms are arranged, depending on convenience to prospective participants to complete evaluation of eligibility, including major clinical depression, detailed medical history and current medications.

Consenting Procedure

The research nurse will obtain verbal consent from the patient agreeing to participate in the screening session. During the screening session, there will be a single informed consent form that describes both the screening and study procedures. Once eligibility is established, Subject's Consent Form and Health Information Privacy Protection Act (HIPAA) information will be reviewed and, if consenting, participants will sign. Each site will have a designated MD or nurse to review documents related to medical and symptom-based eligibility criteria. Informed consent will be documented on a University of Haifa Ethics committee-approved form. A copy of the signed form will be given to the subject. Signed consent forms will be kept in [name] office,

which is an administrative office separate from research data and available for audit even when the PI is not. Additional information contained in a case book will be relevant demographic and medical/psychiatric information about the subject obtained during the interview with the site representative. Because this case book will contain personal identifiers and PHI, it will be kept separate from any data gathered as part of the study, and will be kept in a locked office. After consent is obtained, potential subjects will be screened by study personnel to determine that the subject meets all inclusion and exclusion criteria for study participation.

6.2.2 Enrollment, Baseline, and/or Randomization

Enrollment

Enrollment date is considered immediately following the signing of the consent form after which the enrollment date is recorded in the case book. The participant will be scheduled for a baseline visit in which she will be requested to fill out the baseline questionnaires and provide half an hour of baseline HR and Respiration measurements and 10 ccs of blood. Following this session, the participant will be randomized to the intervention or comparison group.

Baseline Assessments Visit 1 day 0- can be split in to 2 visits to reduce patient burden (see study schema- figure 1)

T1A

DEMOGRAPHICS AND TRADITIONALISM

- A.** We will be collecting baseline demographic data (age, marital status, children (if yes, and how many), religion, religiosity, education, employment, residence (city, village, etc).
- B.** We will measure ethnocultural differences using the Portrait Values Questionnaire (PVQ-RR), which is a 57-item scale consisting of items designed to measure 19 cultural values⁴³. The scale has been validated in 15 samples across 10 countries (n=6059) including Israel. The mean Cronbach α for the tradition values (which we will use as a covariate to enrich the ethno-cultural differences between Jews and Arabs, was 0.8343.

C. CHOLINERGIC ANTI-INFLAMMATORY PATHWAY

A. HRV: 20 minutes of resting ECG data will be recorded. The participants will be given instructions not to drink coffee or smoke for several hours before the lab visit as well as to sit quietly without talking or moving during the ECG recording.

B. Inflammation: We will collect 10 cc's of blood in order to measure immune dysregulation (pro-inflammatory cytokines IL-6, IL-8, IL-1 β , TNF- α), anti-inflammatory (IL-4, IL-10) and regulatory cytokine (TGF- β).

D. PATIENT REPORTED OUTCOMES (PRO):

A. Depression: The **Center for Epidemiologic Studies-Depression (CES-DR)** scale^{71- 10} ITEM SCALE.

B. Fatigue will be assessed using the Fatigue Symptom Inventory (**FSI**)⁷².

C. Pain: The **Breast Cancer Prevention Trial (BCPT) Symptom Scales**⁷³. The **PROMIS Pain Impact Scale**⁷⁴ measures how much pain interfered with different aspects of life in the past 4 weeks.

T1B

A. The **Levels of Emotional Awareness Scale** is a written performance index of variation in the differentiation and complexity of emotional words used to answer the question “how would you feel and how would the other person feel” when presented with 10 evocative scenarios⁷⁵.

B. **Emotional Approach Coping** scales (e.g., **emotional processing, emotional expression**⁷⁶) and **COPE avoidance-oriented coping** subscales (e.g., denial, mental disengagement⁷⁷), all completed with reference to women’s experience of breast cancer.

C. The **Acceptance of Emotions Scale** assesses the extent to which subjects are accepting and nurturing toward their feelings²⁶.

B. Fatigue will be assessed using the Fatigue Symptom Inventory (**FSI**)⁷².

Randomization

Randomization will occur immediately following the baseline visit which will occur within 14 days of the screening visit and one week before the intervention begins. The University statistician will generate numbered envelopes to be opened consecutively as subjects enroll and the envelopes will designate individuals to the intervention through use of a random numbers table.

6.2.3 Blinding

Participants will be blinded to their randomization as will the research nurses and research coordinators.

6.2.4 T 2 – POST intervention

EMOTION PROCESSING

A. The **Levels of Emotional Awareness Scale** is a written performance index of variation in the differentiation and complexity of emotional words used to answer the question “how would you feel and how would the other person feel” when presented with 10 evocative scenarios ^{75,78}.

B. **Emotional Approach Coping** scales (e.g., **emotional processing, emotional expression** ^{79,80}) and COPE **avoidance-oriented coping** subscales⁷⁹ (e.g., denial, mental disengagement), all completed with reference to women’s experience of breast cancer.

C. The **Acceptance of Emotions Scale** assesses the extent to which subjects are accepting and nurturing toward their feelings²⁴.

D. PATIENT REPORTED OUTCOMES (PRO):

A. Depression: The **Center for Epidemiologic Studies-Depression (CES-DR)** scale^{71- 70} ITEM SCALE.

B. Fatigue will be assessed using the Fatigue Symptom Inventory (**FSI**)⁷².

C. Pain: The Breast Cancer Prevention Trial (BCPT) Symptom Scales⁷³. The PROMIS Pain Impact Scale⁷⁴ measures how much pain interfered with different aspects of life in the past 4 weeks.

CHOLINERGIC ANTI-INFLAMMATORY PATHWAY

A. HRV: 20 minutes of resting ECG data will be recorded. The participants will be given instructions not to drink coffee or smoke for 3 hours before the lab visit as well as to sit quietly without talking or moving during the ECG recording.

B. Inflammation: We will collect 10 ccs of blood in order to measure immune dysregulation (pro-inflammatory cytokines IL-6, IL-8, IL-1 β , TNF- α), anti-inflammatory (IL-4, IL-10) and regulatory cytokine (TGF- β).

T3-8 WEEKS AFTER END OF INTERVENTION Completion/Final Evaluation

CHOLINERGIC ANTI-INFLAMMATORY PATHWAY

A. HRV: 20 minutes of resting ECG data will be recorded. The participants will be given instructions not to drink coffee or smoke for 3 hours before the lab visit as well as to sit quietly without talking or moving during the ECG recording.

B. Inflammation: We will collect 10 ccs of blood in order to measure immune dysregulation (pro-inflammatory cytokines IL-6, IL-8, IL-1 β , TNF- α), anti-inflammatory (IL-4, IL-10) and regulatory cytokine (TGF- β).

D. PATIENT REPORTED OUTCOMES (PRO):

A. Depression: The **Center for Epidemiologic Studies-Depression (CES-DR)** scale^{71- 10} ITEM SCALE.

B. Fatigue will be assessed using the Fatigue Symptom Inventory (**FSI**)⁷².

C. Pain: 4 pain specific items to assess pain from the **Breast Cancer Prevention Trial (BCPT) Symptom Scales**⁷³. In addition, we will use the 6 items for pain from the **PROMIS** Pain Impact Scale⁷⁴ measuring how much pain interfered with different aspects of life in the past 4 weeks.

EMOTION PROCESSING

A. The **Levels of Emotional Awareness Scale** is a written performance index of ability to express emotion in a differentiated and complex way.

B. **Emotional Approach Coping** scales (i.e., **emotional processing, emotional expression**⁸⁰ and **COPE avoidance-oriented coping** subscales⁷⁹ (e.g., denial, mental disengagement, all completed with reference to women's experience of breast cancer.

C. The **Acceptance of Emotions Scale** assesses the extent to which subjects are accepting and nurturing toward their feelings²⁴.

7. SAFETY ASSESSMENTS

7.1 Specification of Safety Parameters

N/A

7.2 Methods and Timing for Assessing, Recording, and Analyzing Safety Parameters

N/A

7.3 Adverse Events and Serious Adverse Events

An **adverse event (AE)** is generally defined as any unfavorable and unintended diagnosis,

symptom, sign (including an abnormal laboratory finding), syndrome or disease which either occurs during the study, having been absent at baseline, or if present at baseline, appears to worsen. Adverse events are to be recording regardless of their relationship to the study intervention.

A **serious adverse event (SAE)** is generally defined as any untoward medical occurrence that results in death, is life threatening, requires inpatient hospitalization or prolongation of existing hospitalization, results in persistent or significant disability/incapacity, or is a congenital anomaly.

Adverse events are not expected because of the intervention or comparison groups.

7.4 Reporting Procedures

PI's [name] and [name] will create a **Data and Safety Monitoring Board (DSMB)**, which will meet at approximately six-month intervals. DSMB members will represent expertise in psycho-oncology and in research monitoring. Members of the committee will agree to keep all information confidential. The board members will review summaries of study progress to ensure that consent documentation is properly obtained and stored. They will review progress in subject recruitment and anticipated race/ethnicity participant representation. They will determine whether study coordinators and investigators are collecting and organizing data properly.

7.5 Safety Monitoring

PI [name] will closely monitor and supervise the research team at their respective sites, as well as conduct coordinated oversight of psychological status of all participating women taking part in the research. She will consult with PI [name] with any concern or consideration. PI [name] will also meet regularly with the research teams at the clinical sites and the University every other week to ensure appropriate conduct.

INTERVENTION DISCONTINUATION

Should the PI or site PI discover based on research nurse, patient reports or assessments of outcomes in the initial cohort that the intervention is causing harm rather than benefit (statistically significant mean increases in depression) the intervention will be discontinued.

8. STATISTICAL CONSIDERATIONS

8.1 General Design Issues

A randomized trial with careful controls was chosen to control for the active mechanism of emotion processing that we expect to increase following the art therapy intervention. Our comparison

group is designed to entails aspects of art therapy, such as engaging with art materials and being in a group setting that we believe are not related to the mechanism at hand.

8.2 Sample Size and Randomization

A power analysis was conducted via Monte Carlo simulation in Mplus showed that a sample size of 240 (120 per condition), provides: (1) >90% power to detect a moderate effect size (Cohen's $d = 0.50$) of treatment on mechanisms, (2) >90% power to detect a moderate association ($r = 0.30$) between mechanisms and symptoms, and (3) >90% power to detect an indirect effect from treatment to symptoms via mechanisms. The sample size will also provide >80% power to detect a moderate effect size for the Condition by Ethno-Cultural group interaction.

Consented participants will be randomized into the Art Therapy or Sham condition using block randomization stratified by site, ethnicity and traditionalism to ensure equal sample sizes between groups over time in each site and in each ethnicity. Permutations of group assignment will be generated in random blocks of 4, 6, and 8 so that staff cannot guess the condition of the final participant as the block size varies. Condition assignment will be stored in sealed, numbered envelopes to be opened consecutively as subjects enroll and the envelopes will designate individuals to the intervention through use of a random numbers table. PI [name] will provide the PhD students with the randomized lists (60 each cohort), who will schedule sessions and make weekly calls to encourage attendance, therefore both will be un-blinded to study assignment. The Research Nurse will collect and enter data, collect bio specimens and manage the database, and thus will be un-blinded after randomization. The research assistant (RA) will remain blinded throughout the study, and will receive lists of participants to call, without knowing which group they are assigned to. Participants will be told they are participating in an "art making" study where they will be assigned to an art making group. Participants will not be told which is expected to be superior.

8.3 Treatment Assignment Procedures

Consented participants for each cohort will be randomized (PI- [name]) The University statistician will generate numbered envelopes to be opened consecutively as subjects enroll and the envelopes will designate individuals to the intervention through use of a random numbers table. PI [name] will provide the PhD students with the randomized lists (60 each cohort), who will schedule sessions and make weekly calls to encourage attendance and conduct the intervention and thus will be unblinded. The Research Nurse will collect and enter data, collect bio specimens and manage the database, but will remain blinded after randomization. The research assistant will remain blinded throughout the study, and will receive lists of participants

to call, without knowing which group they are assigned to. Participants will be told they are participating in an “art making” study where they will be assigned to either the intervention group or the sham intervention (Mandala) group. Participants will not be told which is expected to be superior.

Table 4: Roles in the study

Title	Blinded to group assignment	Roles	Rambam	Ziv	Beilinson
Research nurse (employee of each hospital).	Yes	Recruit and obtain verbal consent, collect blood.	1	1	1
Research coordinator (employee of each hospital).	Yes	Assist MD in recruiting patients, collect data (questionnaires and HRV), transfer blood to the lab for processing (separation to serum, divide in 4 aliquots and cryopreservation -80)	1	1	1
Art Therapist	No	Conduct intervention groups (8.5 weeks)- Art Therapy and SHAM in Hebrew or Arabic	2	2	2
PhD student	No	Conduct groups, supervise interventionists, assist in fidelity assurance, assist in data analysis.	3		
Laboratory worker	Yes	Conduct inflammatory cytokines analysis.	1		
Research coordinator	Yes	Coordinate between study site, transport frozen serum to lab, input data	1		

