9. DATA COLLECTION AND QUALITY ASSURANCE

9.1 Data Collection Forms

PI [name] will provide the research coordinators with the randomized lists (60 each cohort), who will schedule sessions and make weekly calls to encourage attendance, therefore both will be un-blinded to study assignment. The Research Nurse will collect and enter data, collect bio specimens and manage the database, and thus will be un-blinded after randomization. The research assistant will remain blinded throughout the study, and will receive lists of participants to call, without knowing which group they are assigned to. Signed

consent forms and all study questionnaires will be kept in an administrative office separate from research data and available for audit even when the PI is not. Additional information contained in this case book will be relevant demographic and medical/psychiatric information about the subject obtained during the interview with the site representative. Because this case book will contain personal identifiers and PHI, it will be kept separate from any data gathered as part of the study and will be kept in a locked office.

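### The Protocol gives the research nurse and the research coordinators opposite blinding status in different sections, and the rules cannot all be followed

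*Protocol*

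**What the plan says.** **Research nurse.** Section 6.2.3 sets the general rule: "Participants will be blinded to their randomization as will the research nurses and research coordinators". Section 8.3 agrees: "The Research Nurse will collect and enter data, collect bio specimens and manage the database, but will remain blinded after randomization". Table 4 also marks her as blinded and gives her role as "Recruit and obtain verbal consent, collect blood". Section 8.2 says the opposite: "The Research Nurse will collect and enter data, collect bio specimens and manage the database, and thus will be un-blinded after randomization". Section 9.1 repeats the 8.2 sentence.

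**Research coordinators.** Section 6.2.3 and Table 4 call them blinded. Table 4 has two coordinator rows. The site coordinators, one per hospital, "collect data (questionnaires and HRV") among other tasks, and one central coordinator inputs data. Section 9.1, however, says that a PI "will provide the research coordinators with the randomized lists (60 each cohort") so that they can book sessions and telephone participants weekly, and concludes: "therefore both will be un-blinded to study assignment". In 8.2 the holders of the same lists are different people: the PI "will provide the PhD students with the randomized lists (60 each cohort"). Section 8.3 agrees with 8.2 on this.

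**Participants.** Sections 5.2 and 6.2.3 say they are blinded. Section 8.2 describes telling them about assignment to an art-making group. Section 8.3 describes telling them that there are two groups, one of them labelled sham and identified with mandalas. Both sections add that women are not told which arm is expected to do better.

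The SAP does not mention blinding.

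**The concern.** A site can follow 6.2.3 and Table 4, or it can follow 9.1, but not both. If it follows 9.1, the coordinators hold the allocation list while, under Table 4, they collect the follow-up questionnaires and heart rate variability recordings or input the data. If it follows 8.2 or 9.1 for the nurse, the person described as entering data and managing the database also knows the arm.

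Knowledge of arm among these staff could affect follow-up data through ordinary routes: how hard a missed visit is pursued, how help with a questionnaire is given, how a resting ECG session is conducted, and how doubtful entries are queried. The Protocol does not describe these steps in enough detail to say whether any of them would matter.

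The participant question is separate and conditional. The measures of emotional expression, acceptance, depression, fatigue and pain are self-reported. A woman who believes she is in a sham arm may answer differently. That would bear on the treatment effect on the mediators (path a in SAP C.5.2), on the indirect effect built from it, and on the treatment effect on symptoms.

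**Working it through.** No formula applies to the contradiction itself, so the statements are set side by side.

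| Role | Stated as blinded | Stated as un-blinded |
|---|---|---|
| Research nurse | 6.2.3, 8.3, Table 4 (3 places) | 8.2, 9.1 (2 places) |
| Research coordinators | 6.2.3, Table 4 site and central rows (2 places) | 9.1 (1 place) |
| Participants | 5.2, 6.2.3 (2 places) | none |

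1. *Nurse.* The sentences in 8.2, 8.3 and 9.1 give the same duties. Two of them draw the conclusion that she is un-blinded and one draws the opposite. No reading satisfies all five places.

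2. *Coordinators.* It is not clear whom the word *both* covers in 9.1, but that does not matter here. A person who holds the randomized list cannot be blinded to it, and 9.1 gives the list to the coordinators.

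3. *List holders.* Sections 8.2 and 8.3 name the PhD students; 9.1 names the coordinators. Table 4 marks the PhD students as not blinded, which fits 8.2 and 8.3.

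4. *Who handles data.* Sections 8.2, 8.3 and 9.1 have the nurse collecting and entering data and running the database. Table 4 gives questionnaires and heart rate variability to the site coordinators, data input to the central coordinator, and blood to the nurse. Table 4 does not say that its role list is complete, so this is an unclear division of work rather than a strict contradiction.

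5. *Reach, from Table 4.* Nurses 1 + 1 + 1 = 3; site coordinators 1 + 1 + 1 = 3; central coordinator 1. Total 3 + 3 + 1 = 7 posts with conflicting status. Section 9.1 does not say which coordinators it means: the count is 3 + 3 = 6 if only the site coordinators, and 3 + 1 = 4 if only the central one.

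6. *Women covered.* Section 9.1 gives 60 per cohort and the study timeline (Table 3) shows 4 cohorts: 60 × 4 = 240, the whole planned sample.

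7. *Participants.* There are two statements that they are blinded (5.2, 6.2.3) and two differing descriptions of what they are told (8.2, 8.3). Section 5.2 has comparison participants colour mandalas for 40 minutes per session. If the 8.3 description is read to women, someone colouring mandalas could recognise the arm described to her as the sham.

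The counts in steps 5 and 6 measure how far the contradiction extends. They do not measure bias.

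**The case against.** The strongest reply is that the staff conflict may do little harm. Most symptom and coping measures are answered by the woman herself, the laboratory worker who assays the cytokines is blinded in Table 4, and baseline is collected before randomization (6.2.2). This stands in part: it limits the exposure to follow-up collection and handling, and it is why no bias is quantified. It does not reconcile the sections.

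A second reply is that 8.2 and 9.1 give a working reason for un-blinding the nurse, namely her data and database duties, so declaring her blinded may not be workable. This also stands in part. The declaration is credible only if the allocation is kept out of the database she uses, and the Protocol does not describe that database.

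A third is that leaving the lists with the PhD students does not make everyone near the data blinded, since Table 4 has those un-blinded students assist with analysis. That is true, and the change proposed here does not resolve it.

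On participants, a reader might infer that the Protocol un-blinds them, or that 8.2 and 8.3 are flat opposites. The documents do not support either. No section calls participants un-blinded. Section 8.2 does not say that the art-making description is all they hear, and its remark about superiority implies they know of more than one group. The arm names in 8.3 may be the Protocol's own labels rather than words spoken to women. The 4.2 script and the consent form, which would settle this, are not in the copy reviewed, and their absence is not a fault of the plan.

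**Conclusion.** The staff contradiction is certain. It stands in the current text and rests on no assumption. It concerns up to 7 posts (6 or 4 on narrower readings of 9.1) and lists that cover all 240 planned women. Under 9.1 as written, staff who collect or enter outcome data would know the allocation. The direction and size of any bias are unknown, and sample size and power are unaffected. It should be fixed.

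A reader might go further and conclude that outcome data will be biased, or that Table 4 bars the nurse from data work. Neither follows: the documents show conflicting instructions, not what sites do, and Table 4 is a role summary that does not claim to be exhaustive.

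The participant point holds only if the 8.3 description is what women are actually told. Even with neutral wording some expectancy could remain, because the sessions differ visibly.

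**What to change.** 1. In 9.1, give the randomized lists to the PhD students, as 8.2 and 8.3 do, and remove the statement that coordinators are un-blinded.
2. In 8.2 and 9.1, state that the nurse remains blinded after randomization, in line with 6.2.3, 8.3 and Table 4.
3. State that the allocation is held outside the outcome database that blinded staff enter or manage. This answers the reason 8.2 and 9.1 give for un-blinding the nurse.
4. State once who collects and who enters each type of outcome data, and make 8.2, 8.3, 9.1 and Table 4 agree.
5. Reconcile 8.3 with 5.2, 6.2.3 and 8.2 by describing the groups in arm-neutral terms and keeping the statement about superiority. Check the 4.2 script and the consent form against that wording. Any change must still meet the explanation required at consent in 9.2 and needs ethics approval under 10.1.

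The cost is a wording amendment and its ethics review. No new staff are needed, because the Protocol already assigns list-holding and data collection to existing roles. The script and consent form change only if they carry the 8.3 description. Separating the allocation from the database is a matter of file access; it cannot be costed because the database is not described.
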